9.7 Concomitant medication/procedure

The listing “Concomitant medication/procedure” will include the following information:

- Center
- Patient id.
- Treatment arm (Arm A; Arm B; Arm C)

- Medication / procedure (Yes/no)
- Medication / procedure description
- Use (Prophylactic; Therapeutic)
- Description: Active substance/Procedure
- Code (ATC)
- Start date
- Ongoing (Yes/No)

- End date
- Dose
- Units (mg; µg; mL; g; IU; Other)
 - Other: specify
- Frequency (2 times a day; 3 times a day; 4 times a day; A demand; Every 24 hours; Monthly Weekly; Daily; Every hour; Every 2 hours; Other)
 - Other: specify
- Route of administration (Oral; Topical; Subcutaneous; Transdermal; Intraocular; Intramuscular; Intravenous; Respiratory (inhaled); Intraperitoneal; Nasal; Other.)
 - Other: specify
- Indication (study disease; Concomitant disease; Adverse event; Other)
 - Adverse event: specify
 - Other: specify

9.8 End of study

The listing “End of study” will include the following information:

- Center
- Patient id.
- Treatment arm (Arm A; Arm B; Arm C)
- End of study (yes/no)
- End of study reason (Follow-up completed according to protocol; Withdrawal by subject; Lost to Follow-up; Death; the patient was randomized but did not receive the study drug; Investigator's decision; Early end of study; Other).
 - Lost to Follow-up: date.
 - The patient was randomized but did not receive the study drug: specify.
 - Investigator's decision: specify.
 - Early end of study: specify.
 - Other: specify.
- Follow-up time: defined as the time, in days, between the informed consent signing date until the end of study date by the patient. If the study has not been completed at the time of the analysis, the date of the last follow-up of the patient will be taken.

9.9 Deaths

The listing “Deaths” will include the following information:

- Center
- Patient id.
- Treatment arm (arm A; Arm B; Arm C)
- End of treatment (yes/no)

- Main cause of death (Acute respiratory distress syndrome (ARDS); Adverse event not related to treatment; Adverse reaction to plitidepsin; Unknown; Other)
 - Adverse event not related to treatment: the description of the event and the grade (1; 2; 3; 4; 5; Not available) will be provided.
 - Adverse reaction to plitidepsin, description of toxicity and grade will be provided (1; 2; 3; 4; 5; Not available).
 - Other: specify

9.10 Protocol deviations

The listing will include the following information:

- Center
- Deviation date
- Related patient
- Category (Minor; Major; Critical)
- Deviation (Selection criteria; Informed consent; Investigational drug; Safety; Efficacy criteria; Others)
- Reason (text)

APPENDIX I

10 STUDY POPULATION

10.1 Patient disposition

Table 10.1.1 Subject Disposition

Disposition	Dose Cohort			
	1.5 mg N=X	2.0 mg N=X	2.5 mg N=X	Total N=X
	n (%)			
Included Population				
Safety Population				
Efficacy Population				
Completed 3-day treatment				
Completed Day 31 follow-up				

Listing 10.1.2 Patients included but not treated.

Patient id.	Description

Table 10.1.3 Subject Disposition by site

Sites	Dose Cohort							
	1.5 mg N=X		2.0 mg N=X		2.5 mg N=X		Total N=X	
	n (%)							
	Included	Treated	Included	Treated	Included	Treated	Included	Treated
Site 1								
Site 2								
Site ...								

Table 10.1.4 Study dates

	Total
Date of first registration	
Date of first dose of the first patient	
Date of last registration	
Date of first dose of the last patient	
Date of last dose	
Date of last follow-up*	

(*) Last follow-up, exam or procedure before clinical cut-off or study closure

Table 10.1.5 Treatment discontinuation

Reason	Dose Cohort			
	1.5 mg N=X	2.0 mg N=X	2.5 mg N=X	Total N=X
	n (%)			
Primary reason for treatment discontinuation prior to Day 31 safety follow-up:				
Adverse event				
Death				
...				

Table 10.1.6 Off-study

	Dose Cohort			
	1.5 mg N=X	2.0 mg N=X	2.5 mg N=X	Total N=X
	n (%)			
Off study reasons				
Completed				
Lost to Follow -up				
Withdrawal of consent				
...				

10.2 Patient description

Table 10.2.1 Demographic and Other Baseline Characteristics

	Dose Cohort			
	1.5 mg N=X	2.0 mg N=X	2.5 mg N=X	Total N=X
Age, median (range) years				
Gender, % male				
Median (range) time from symptom onset to first administration, days				
Number of comorbidities, n (%)				
None				
One				
Two or more				
Comorbidities, n (%)				
Cardiac disease				
Kidney disease				
Liver disease				
Lung disease (COPD)				
Asthma				
Diabetes				
Hypertension				
Obesity				
Clinical status at baseline, n (%)				
Mild COVID-19 infection				
Moderate COVID-19 infection				
Severe COVID-19 infection				
Vital signs, median (range)				
Body temperature, °C				
Systolic blood pressure, mmHg				
Diastolic blood pressure, mmHg				
Heart rate, bpm				
Respiratory rate, bpm				
SpO ₂ at room air, %				
On oxygen at baseline, n (%)				
Laboratory parameters, median (range)				
WBC, x10 ⁹ /L				
Platelet count, x10 ⁹ /L				
Lymphocytes, x10 ⁹ /L				
Serum creatinine, µmol/L				
ALT, x ULN				
AST, x ULN				
LDH, x ULN				

	Dose Cohort			
	1.5 mg N=X	2.0 mg N=X	2.5 mg N=X	Total N=X
GGT, x ULN				
CPK, x ULN				
Ferritin (ng/mL)				
D-dimer (ng/mL)				
C-reactive protein (mg/L)				
log ₁₀ viral load, median (range) copies/mL				

(*) Further covariates could be added upon request

Table 10.2.2 Demographic Baseline Characteristics (continuous variables)

	Dose Cohort																	
	1.5						...						Total					
	N	Mean	Median	Range	Q1	...*	N	Mean	Median	Range	Q1	...*
Age																		

(*) Q3 and Std.

Table 10.2.3 Clinical data (Signs and symptoms on admission) Baseline Characteristics (continuous variables)

	Dose Cohort																	
	1.5						...						Total					
	N	Mean	Median	Range	Q1	...*	N	Mean	Median	Range	Q1	...*
**																		

(*) Q3 and Std.

(**) Onset first symptom to signing of IC; Onset first symptom to first dose of treatment, Onset first symptom to first PCR

Table 10.2.4 Vital signs Baseline Characteristics (continuous variables)

	Dose Cohort																	
	1.5						...						Total					
	N	Mean	Median	Range	Q1	...*	N	Mean	Median	Range	Q1	...*
**																		

(*) Q3 and Std.

(**) SBP, DBP, Heart rate, Respiratory rate, Temperature, Saturation O₂, Flow FiO₂, PaO₂, PaO₂/FiO₂ or SaO₂/FiO₂

Table 10.2.5 Demographic Baseline Characteristics (categorical variables)

n (%)	Dose Cohort			
	1.5 mg N=X	2.0 mg N=X	2.5 mg N=X	Total N=X
*				

(*) Gender (Male/Female); Age (<65/>=65); Ethnic group

Table 10.2.6 Clinical data (Signs and symptoms on admission) Baseline Characteristics

n (%)	Dose Cohort			
	1.5 mg N=X	2.0 mg N=X	2.5 mg N=X	Total N=X
*				

(*) Time from the beginning of the first symptom to hospital admission, Time from hospital admission to first dose of plitidepsin treatment, Fever, Dehydration, Cough, Sputum production, Hemoptysis, Runny nose, Earache, Crackles, Thoracic Pain, Muscular pain, Joint pain, Fatigue, Short of breathe, Intercostal retraction, Headache, Confusion, Convulsion, Abdominal pain, Vomiting\Nausea, Diarrhea, Conjunctivitis, Rash, Skin ulcer, Lymphadenopathy, Throat pain, Bleeding.

Table 10.2.7 Clinical data (Comorbidities) Baseline Characteristics (categorical variables)

n (%)	Dose Cohort			
	1.5 mg N=X	2.0 mg N=X	2.5 mg N=X	Total N=X
*				

(*)Chronic Cardiac pathologies, Arterial Hypertension, Chronic lung disease, Asthma, Diabetes with complications, Diabetes without complications, Chronic kidney disease, Rheumatic disorder, Moderate or severe liver disease, Mild liver disease, Dementia, Malnutrition, Chronic neurological disorder, Smoker, Malignant neoplasm, Chronic hematological disease, AIDS, obesity, Other risk factors, Other details.

Table 10.2.8 Vital signs at baseline Characteristics (categorical variables)

n (%)	Dose Cohort			
	1.5 mg N=X	2.0 mg N=X	2.5 mg N=X	Total N=X
*				

(*) Saturation, Oxygen therapy type, Chest X-Ray, Electrocardiogram, Result, FDA classification

Table 10.2.9 Six-point ordinal scale on Day 1

n (%)	Dose Cohort			
	1.5 mg N=X	2.0 mg N=X	2.5 mg N=X	Total N=X
1 Discharge (Alive)				
2 Hospital admission, not requiring supplemental oxygen				
...				

Table 10.2.10 Days with symptoms according to baseline viral load

	Viral Load at baseline (copies/mL)			p-value(*)
	Low <4	Medium [4-7]	High >7	
Days with symptoms				

(*) Kruskal-Wallis

APPENDIX II

11 SAFETY EVALUATION

11.1 Safety endpoints

Table 11.1.1 Summary of Protocol-Specified Safety Endpoints. Cumulative results.

Endpoint	Dose Cohort			
	1.5 mg N=X	2.0 mg N=X	2.5 mg N=X	Total N=X
	n (%)			
Patients unable to complete treatment				
Patients with grade ≥ 3 AEs from Day 1 to				
Day 3				
Day 7				
Day 15				
Day 31				
Patients with AEs from Day 1 to				
Day 3				
Day 7				
Day 15				
Day 31				
Patients with SAEs from Day 1 to				
Day 3				
Day 7				
Day 15				
Day 31				
Patients with ≥ 1 grade change in hematological parameters from Day 1 to				
Day 3				
Day 7				
Day 15				
Day 31				
Patients with ≥ 1 grade change in non-hematological parameters, from Day 1 to				
Day 3				
Day 7				
Day 15				
Day 31				
Patients with QTc >60msec from baseline to				
Day 31				

This table will be also performed by age (<65 vs. ≥ 65 year old (11.1.1.1))

Table 11.1.2 Summary of Protocol-Specified Safety Endpoints. Non-cumulative.

Endpoint	Dose Cohort			
	1.5 mg N=X	2.0 mg N=X	2.5 mg N=X	Total N=X
	n (%)			
Patients unable to complete treatment				
Patients with grade ≥ 3 AEs from				
Day 1 to Day 3				
Day 4 to Day 7				
Day 8 to Day 15				
Day 16 to Day 31				
Patients with AEs from				
Day 1 to Day 3				
Day 4 to Day 7				
Day 8 to Day 15				
Day 16 to Day 31				
Patients with SAEs from				
Day 1 to Day 3				
Day 4 to Day 7				
Day 8 to Day 15				
Day 16 to Day 31				
Patients with ≥ 1 grade change in hematological parameters from				
Day 1 to Day 3				
Day 4 to Day 7				
Day 8 to Day 15				
Day 16 to Day 31				
Patients with ≥ 1 grade change in non- hematological parameters, from				
Day 1 to Day 3				
Day 4 to Day 7				
Day 8 to Day 15				
Day 16 to Day 31				

This table will be also performed by age (<65 vs. ≥ 65 year old) (11.1.2.1)

11.2 Treatment administration

Table 11.2.1 Administered Doses

Administered Doses, n (%)	Dose Cohort			
	1.5 mg N=X	2.0 mg N=X	2.5 mg N=X	Total N=X
Day 1				
Day 2				
Day 3				

This table will be also performed by age (<65 vs. ≥ 65 year old) (11.2.1.1)

Table 11.2.2 Administered dose interrupted

Administered dose interrupted	1.5 mg		2 mg		2.5 mg		Total	
	N	%	N	%	N	%	N	%
Reason								

This table will be also performed by age (<65 vs. ≥ 65 year old) (11.2.2.1)

Table 11.2.3 Total administered dose

	Dose Cohort																	
	1.5						...						Total					
	N	Mean	Median	Range	Q1	...#	N	Mean	Median	Range	Q1	...*
Total dose (mg)																		

This table will be also performed by age (<65 vs. >=65 year old) (11.2.3.1)

Table 11.2.4 Relative dose intensity

	Dose Cohort																	
	1.5						...						Total					
	N	Mean	Median	Range	Q1	...#	N	Mean	Median	Range	Q1	...*
Relative dose intensity (%)																		

This table will be also performed by age (<65 vs. >=65 year old) (11.2.4.1)

11.3 Premedication

Table 11.3.1 Administered Premedication

Premedication		1.5 mg		2.0 mg		2.5 mg		Total	
		N=X		N=X		N=X		N=X	
		N	%	N	%	N	%	N	%
Day 1	Yes								
Day 2	Yes								
Day 3	Yes								

Table 11.3.2 Premedication

Premedication*		1.5 mg		2.0 mg		2.5 mg		Total	
		N=X		N=X		N=X		N=X	
		N	%	N	%	N	%	N	%
ATC1	ATC2								
	ATC2								
ATC1	ATC2								

(*)More ATC levels could be displayed upon request.

11.4 Adverse events

Table 11.4.1 Summary of Adverse Events, Regardless of Relationship, by SOC and PT by Dose Cohort and Overall

MedDRA SOC Preferred Term	Dose Cohort			
	1.5 mg N=X	2.0 mg N=X	2.5 mg N=X	Total N=X
	n (%)			
Subjects with any AE				
Gastrointestinal disorders				
Abdominal pain				
Abdominal pain upper				
....				
General disorders and administration site conditions				
Asthenia				
Chest discomfort				
...				

Each patient reported once per Preferred Term; This table will be also performed by age (<65 vs. ≥65 year old) (11.4.1.1)

Listing 11.4.2 All adverse events

Dose cohort	Subject id.	Age	SOC	PT	Serious adverse events	Relationship	Grade	Onset date	End date

Table 11.4.3 Summary of Treatment-Related Adverse Events by SOC and PT by Dose Cohort and Overall

MedDRA SOC Preferred Term	Dose Cohort			
	1.5 mg N=X	2.0 mg N=X	2.5 mg N=X	Total N=X
	n (%)			
Subject with any related AE				
Gastrointestinal disorders				
Abdominal pain				
Abdominal pain upper				
....				
General disorders and administration site conditions				
Asthenia				
Chest discomfort				
...				

Each patient reported once per Preferred Term; This table will be also performed by age (<65 vs. ≥65 year old) (11.4.3.1)

Listing 11.4.4 All Related Adverse Events

Dose cohort	Subject id.	Age	SOC	PT	Serious adverse events	Relationship	Grade	Onset date	End date

Table 11.4.5 Grade ≥3 Adverse Events, Regardless of Relationship by Dose Cohort and Overall

MedDRA SOC Preferred Term	Dose Cohort			
	1.5 mg N=X	2.0 mg N=X	2.5 mg N=X	Total N=X
	n (%)			
Patients with any Grade ≥3 AE				
Blood and lymphatic system disorders				
Leukocytosis				
Gastrointestinal system disorders				
Diarrhea				

Each patient reported once per Preferred Term; This table will be also performed by age (<65 vs. ≥65 year old) (11.4.5.1)

Table 11.4.14 Summary of Adverse Events

Patients	1.5 mg N=X		2.0 mg N=X		2.5 mg N=X		Total N=X	
	N	%	N	%	N	%	N	%
Patients with AEs								
Patients with treatment-related AEs								
Patients with Grade >=3 AEs								
Patients with Grade >=3 treatment-related AEs								
Patients with SAEs								
Patients with treatment-related SAEs								

This table will be also performed by age (<65 vs. >=65 year old) (11.4.14.1)

Listing 11.4.15 Patients Experiencing AEs Leading treatment discontinuation or drug interruption

Dose Cohort	Subject id	Sex	Age	AE treatment discontinuation/Interruption	Relatedness	Study Day of Onset/Death

11.5 Serious Adverse events and Death

Listing 11.5.1 SAEs Regardless of Relationship

Dose cohort	Subject id.	Age	SOC	PT	Relationship	Grade	Onset date	End date

Listing 11.5.2 SAEs Related

Dose cohort	Subject id.	Age	SOC	PT	Relationship	Grade	Onset date	End date

Listing 11.5.3 Patients Experiencing SAEs Leading treatment discontinuation

Dose Cohort	Subject id	Sex	Age	TEAE treatment discontinuation	Relatedness	Study Day of Onset/Death

Listing 11.5.4 Patients Experiencing Serious Adverse Events (SAEs) Not Resulting in Death

Dose Cohort	Subject id	Sex	Age	SAE event	Action	Relatedness	Study Day of Onset/Resolution

Table 11.5.5 Death

Death n (%)	Dose Cohort			
	1.5 mg N=X	2.0 mg N=X	2.5 mg N=X	Total N=X
Death				

Listing 11.5.6 Patients Experiencing SAEs Leading to Death

Dose Cohort	Subject id	Sex	Age	TEAE Leading to Death	Relatedness	Day of Death

11.6 Laboratory

Table 11.6.1 Shift in Hematology Parameters from Baseline to Greatest Change in Grade on Study for Combined Dose Groups

Parameter	Grade at Baseline	Grade Change per Patient on Study				
		0	1	2	3	Total
Anemia (hemoglobin)	0					
	1					
Leukopenia (leukocytes)	0					
	1					
	...					
.....						

This table will be also performed by age (<65 vs. >=65 year old) (11.6.1.1)

This table will be also performed by inflammatory parameters (11.6.1.2)

Laboratory table by pre&post amendment (13AUG2020) will be generated upon request. (11.6.1.3)

This table will be also performed by pre&post amendment (13AUG2020) (11.6.1.4)

Table 11.6.2 Shift in Chemistry Parameters from Baseline to Greatest Change in Grade on Study for Combined Dose Groups Percentages are shown for changes from baseline

Parameter	Grade at Baseline	Grade Change per Patient on Study				
		0	1	2	3	Total
ALT increased	0					
	1					
AP increased	0					
	missing					
AST increased	0					
	1					
.....					

This table will be also performed by age (<65 vs. >=65 year old) (11.6.2.1)

This table will be also performed by pre&post amendment(13AUG2020) (11.6.2.2)

Listing 11.6.3 Hematological laboratory parameters

Subject ID	Visit	Date	...(*)	change (%)	...()	change (%)
.....	Baseline					
	Day 3					
	...					

(*) Hematological parameters

Listing 11.6.4 Coagulation laboratory parameters

Subject ID	Visit	Date	...(*)	change (%)	...()	change (%)
.....	Baseline					

Subject ID	Visit	Date	...(*)	change (%)	...()	change (%)
	Day 3					
	...					

(*) Coagulation parameters

Table 11.6.5 Biochemical laboratory parameters

Subject ID	Visit	Date	...(*)	change (%)	...()	change (%)
.....	Baseline					
	Day 3					
	...					

(*) Biochemical parameters

Listing 11.6.6 Laboratory abnormalities reported in AE form

Dose Cohort	Subject id	AE	PT	SOC	Action	Relatedness	Study Day of Onset/Resolution

11.7 Vital signs, ECG and Chest X-Ray

Table 11.7.1 Change in Vital Signs from Baseline through Day 31

Parameter*	Dose Cohort			
	1.5 mg N=X	2.0 mg N=X	2.5 mg N=X	Total N=X
Blood pressure, diastolic (mm Hg), median (range)				
Baseline				
Change at Day 1				
Change at Day 2				
Change at Day 3				
Change at Day 7				
Change at Day 15				
Change at Day 31				
Blood pressure, systolic (mm Hg), median (range)				
Baseline				
Change at Day 1				
Change at Day 2				
Change at Day 3				
Change at Day 7				
Change at Day 15				
Change at Day 31				
Heart rate (beats per minute), median (range)				
Baseline				
Change at Day 1				
Change at Day 2				
Change at Day 3				
Change at Day 7				
Change at Day 15				
Change at Day 31				
Respiratory rate (breaths per minute), median (range)				
Baseline				
Change at Day 1				
Change at Day 2				
Change at Day 3				
Change at Day 7				
Change at Day 15				
Change at Day 31				
pSO2** by pulse oximetry (%), median (range)				
Baseline				
Change at Day 1				
Change at Day 2				

Table 11.7.5 Shift in QTc Data from Baseline to Worst Result on Treatment

Baseline Result	Worst Post-Baseline Result						Total
	Normal	QTc >450ms	QTc >480ms	QTc >500ms	QTc >30ms from baseline	Other abnormality	
Combined cohorts:							
Normal							
QTc>450ms							
QTc>480ms							
QTc>500ms							
Other abnormality							
Total							

This table will be also performed by age (<65 vs. >=65 year old) (11.7.5.1)

Listing 11.7.6 SaO2 evolution

Subject ID	Visit	Date	Time	Type of oxygen saturation	SaO2 (%)
	Baseline		
	Day 1		...	Room air	

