3 GENERAL PRINCIPLES

Planned analyses in this document will be carried out once the database is declared cleaned, closed and approved by Pharma Mar according to the premises described in the Data Management Plan version 2.0 approved on 09 June 2020.

Statistical analyses will be performed using SAS software version 9.4 and R. The results of the analyses will be presented in editable format (i.e rtf).

The data will be provided with one decimal place in general. In those cases where greater precision is required, as many decimal places as necessary will be provided.

Before to perform the analyses, the following activities will be performed:

Codification/revision and approval of the following terms:

- Adverse events /procedures according to MedDRA dictionary (latest version available).
- Medication according to the WhoDrug dictionary (latest version available).
- Reconciliation of serious adverse events in the study between the clinical database and the Pharmacovigilance database and resolution of all discrepancies.

Analysis will be done separately for each arm and the total population.

Continuous variables will be presented through the mean, median, standard deviation, range, Q1, Q3 and categorical variables will be presented through the distribution of frequencies and percentages; missing values will not be taken into account in the percentage calculation, percentages with valid data will be presented.

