7 SAFETY EVALUATION

The safety analysis will be performed on the safety population defined in section 4.1. They will be presented by treatment arm as well as by treatment arm based on age groups (<65 years; ≥ 65 years) and the total population.

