7.1 Safety evaluation. General considerations

Adverse events will be coded by using MedDRA (latest version available) and will be presented grouped by system (SOC) and preferred term (PT). The associated grades with each of the adverse events will be evaluated using the NCI-CTCAE V5.0 toxicity criteria.

To obtain the adverse events per patient, the maximum grade will be considered for each of the events collected for each patient. If the relationship between an adverse event and the study drug cannot be ruled out, it will be considered to be related for the analysis.

The analysis will be presented on days 3, 7, 15 and 31 after the start of study treatment:

The following results will be provided:

- Number and percentage of patients presenting the following adverse events with ≥ 1 grade change in:
 - Hematological parameters:
 - Neutropenia
 - Thrombocytopenia
 - Anemia
 - Lymphopenia
 - Non-hematological parameters:
 - CPK increase
 - AST increase
 - ALT increase
 - Total increase, or direct bilirubin
 - Neurotoxicity
 - QT-QTc interval prolongation
- Number and percentage of patients unable to complete treatment
- The number and percentage of patients with some AE or SAE will be presented:
 - From Day 1 to day 3
 - From Day 1 to day 7
 - From Day 1 to day 15
 - From Day 1 to day 31
- The number and percentage of patients with some SAE will be presented:
 - From Day 1 to day 3
 - From Day 1 to day 7
 - From Day 1 to day 15
 - From Day 1 to day 31
- The number and percentage of patients with some Grade ≥ 3 Adverse Events, Regardless of Relationship will be presented.
 - From Day 1 to day 3

- From Day 1 to day 7
 - From Day 1 to day 15
 - From Day 1 to day 31
- Patients with ≥ 1 grade change from baseline in hematologic parameters, from Day 1 to.
 - From Day 1 to day 3
 - From Day 1 to day 7
 - From Day 1 to day 15
 - From Day 1 to day 31
 - Patients with ≥ 1 grade change from baseline in non-hematologic parameters, from Day 1 to
 - From Day 1 to day 3
 - From Day 1 to day 7
 - From Day 1 to day 15
 - From Day 1 to day 31
 - The number and percentage of patients with some Treatment-Related Adverse Events will be presented.
 - The number and percentage of Treatment-Related Adverse Events will be presented.
 - The number and percentage of Adverse Events, Regardless of Relationship, by grade will be presented.
 - The number and percentage of patients with some grade ≥ 3 Adverse Events, Regardless of Relationship will be presented.

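### SAP Table 11.7.5 mixes absolute QTc limits with a >30 ms rise from baseline, gives no counting rule, and is pooled over doses in its visible shell

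*SAP*

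**What the plan says.** Table 11.7.5 (SAP 11.7) is titled "Shift in QTc Data from Baseline to Worst Result on Treatment". Its post-baseline columns are normal, QTc >450, >480 and >500 ms, "QTc >30ms from baseline", other abnormality, and a total. The baseline rows repeat the absolute limits but have no counterpart to the change column. The visible block is labelled "Combined cohorts", and the only repeat noted beneath it is by age (11.7.5.1).

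The SAP's general rules ask for results by dose. Section 3 says: "Analysis will be done separately for each arm and the total population". Section 7 says of the safety analyses: "They will be presented by treatment arm as well as by treatment arm based on age groups". Protocol 12.1 likewise requires results by arm, and the primary objective is safety at each dose level.

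QTc also appears elsewhere, by arm:
- Table 11.1.1 has a row "Patients with QTc >60msec from baseline to" Day 31, with one column per dose and a total.
- SAP 7.1 lists "QT-QTc interval prolongation" among the events to be summarised, and Table 11.4.5 gives grade 3 or higher adverse events by dose.
- SAP 7.3 plans counts and descriptions of ECG alterations by arm at baseline and on days 1 to 7, 15 and 31.

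**The concern.** A shift table works when each patient has one baseline category and one post-baseline category. Here the absolute limits are open-ended and nested, and the change criterion can be met together with any of them. Without a counting rule, the >30 ms count and the row totals cannot both be relied on, and a reader of the finished table could not tell which convention was used.

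Pooling adds a separate problem. The trial is meant to describe safety at each of three doses and to support a dose choice. A dose pattern in the measured QTc shift cannot be seen in a table that adds the three doses together.

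**Working it through.** The plan states no figure that depends on this table, so there is nothing to reproduce. The check is of the shell's logic, followed by two illustrations.

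**Inputs from the documents.** The columns are those of Table 11.7.5. QTc of 450 ms or more is an exclusion (criterion 17 in Protocol 7.2 and SAP 2.9). There are 15 patients per dose and 45 in total (SAP 2.4).

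**Step 1: which columns a patient meets.** Four invented patients, with rise = worst minus baseline:

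| Patient | Baseline (ms) | Worst (ms) | Rise (ms) | Columns met |
|---|---|---|---|---|
| 1 | 440 | 455 | 15 | >450 |
| 2 | 415 | 455 | 40 | >450, >30 rise |
| 3 | 440 | 485 | 45 | >450, >480, >30 rise |
| 4 | 440 | 505 | 65 | >450, >480, >500, >30 rise |

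**Step 2: the overlap forced by eligibility.** If baseline is below 450 ms and the worst value is above 480 ms, the rise exceeds 480 - 450 = 30 ms. Above 500 ms it exceeds 500 - 450 = 50 ms. Every such patient meets the >30 ms criterion as well as an absolute one.

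**Step 3: the four patients under the possible rules.**
- Counted once, absolute limit first: the >30 ms column shows 0, although three patients rose by more than 30 ms.
- Counted once, change first: the >30 ms column is right, but the absolute columns lose patients 2, 3 and 4.
- Highest absolute limit plus the change column: 1 + 2 + 2 + 2 = 7 entries for 4 patients.
- Every column met: 1 + 2 + 3 + 4 = 10 entries for 4 patients.

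No rule gives a correct count in every column and columns that add to the number of patients.

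**Step 4: how common the overlap could be.** The documents give no QTc distribution, so these inputs are assumptions: baseline normal with mean 400, 415 or 430 ms and SD 18 ms, cut off below 450 ms; worst change normal with mean 10 or 20 ms and SD 15 or 20 ms. By simulation, the share of >30 ms rises that also exceed 450 ms runs from 24% (means 400 and 10, change SD 15) to 85% (means 430 and 20, change SD 20). The expected number of patients meeting both criteria is 45 x 0.022 = 1.0 to 45 x 0.261 = 11.7.

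**Step 5: the effect of pooling.** Hypothetical cases all in one arm, with exact (Clopper-Pearson) 95% intervals:

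| Cases | In the arm | Pooled |
|---|---|---|
| 2 | 2/15 = 13.3% (1.7 to 40.5) | 2/45 = 4.4% (0.5 to 15.1) |
| 3 | 3/15 = 20.0% (4.3 to 48.1) | 3/45 = 6.7% (1.4 to 18.3) |

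Three pooled cases look the same whether they fall one per arm or all in one arm.

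**The case against.** The strongest reply is that this is a mock shell with an ordinary reading. Worst result across ascending limits means the highest limit reached, so a patient at 485 ms goes under >480 and not also under >450. On that reading only the change column is ambiguous. By Step 2, patients with baseline below 450 ms who appear under >480 or >500 can be recognised as having risen by more than 30 ms. This stands as far as it goes. It leaves the range from just above 450 to 480 ms unresolved: patients 1 and 2 share one cell, and only one of them rose by more than 30 ms. It also does not say what the change column holds.

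A second reply is that the by-arm rule in SAP 3 may govern how the shell is filled, and that Tables 11.7.2 to 11.7.4 are not in the text available. Both are fair. Nothing can be said about those tables, and the pooling point is limited to the visible shell. Still, the shell names one pooled block and a repeat by age only. Tables 12.1.33 and 12.1.35 carry a note that a split by dose can be requested; this one does not.

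A third reply is that the named primary endpoint is grade 3 or higher QT-QTc prolongation, an adverse-event count reported by dose in Table 11.4.5. That is correct. The other outputs do not replace the measured shift, however. Table 11.1.1 has only the >60 ms threshold, and its row for non-haematological grade changes combines QTc with other parameters. An abnormal ECG is recorded as an adverse event only if the investigator judges it clinically relevant (Protocol 11.2.5). SAP 7.3 sets no QTc thresholds.

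**Conclusion.** The point holds for Table 11.7.5 as shown. Its columns overlap, no counting rule is given, and the visible shell is pooled. The >30 ms rise and the shifts past 450, 480 and 500 ms therefore have no visible by-dose result.

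Three stronger readings are not supported:
- **QTc rises are undercounted.** That is one possible outcome. If patients are entered in every column they meet, the columns overcount instead.
- **QTc is not reported by dose.** Rises above 60 ms, prolongation events and ECG alterations are all planned by arm.
- **Each affected patient costs 1/15 = 6.7 percentage points.** In the pooled table one patient is 1/45 = 2.2%; the 6.7 points apply only once the table is split by dose.

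The size of the miscount is unknown. The 24% to 85% range rests entirely on assumed QTc distributions. The forced overlap above 480 ms rests only on a baseline below 450 ms, as eligibility requires. The table is descriptive and feeds no test or stopping rule, so this is a reporting defect worth correcting rather than a threat to the primary endpoint.

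**What to change.** Replace Table 11.7.5 with two tables, each with columns for 1.5, 2.0 and 2.5 mg plus total, and each counting every patient once:
- Worst post-baseline QTc in exclusive bands: <=450, 451-480, 481-500 and >500 ms.
- Maximum increase from baseline: <=30, 31-60 and >60 ms. This also brings the >30 ms criterion here and the >60 ms criterion of Table 11.1.1 onto one scale.

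Other ECG abnormalities can stay with the by-arm summary in SAP 7.3. A footnote should state which ECG days count, because the present title says on treatment, dosing lasts 3 days, and ECGs run to day 31. The repeat by age can be kept.

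The cost is one extra table shell and its programming. The ECGs are already scheduled, so no new data are needed.
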